#### 10.1.2.1. Serious Adverse Events

Planned surgeries should not be reported as SAEs unless the underlying medical condition has worsened during the course of the study.

Planned hospitalizations or elective procedures for underlying preexisting conditions that are already recorded in the patient's medical history at the time of study enrollment should not be considered SAEs. Hospitalization or prolongation of hospitalization without a precipitating clinical AE (for example, for the administration of study therapy or other protocol-required procedure) should not be considered SAEs.

An SAE is any AE during this study that results in one of the following outcomes:

- death
- initial or prolonged inpatient hospitalization (except for study drug administration)
- a life-threatening experience (ie, immediate risk of dying)
- persistent or significant disability/incapacity
- congenital anomaly/birth defect
- considered significant by the investigator for any other reason.

Important medical events that may not result in death, be life-threatening, or require hospitalization may be considered SAEs when, based on appropriate medical judgment, they may jeopardize the patient and may require medical or surgical intervention to prevent one of the outcomes listed in this definition.

Serious adverse events due to disease progression, including death, should not be reported unless the investigator deems them to be possibly related to the study drug.

Study site personnel must alert Lilly or its designee of any SAE within 24 hours of investigator awareness of the event via a sponsor-approved method. If alerts are issued via telephone, they are to be immediately followed with official notification on study-specific SAE forms. This 24-hour notification requirement refers to the initial SAE information and all follow-up SAE information.

If an investigator becomes aware of SAEs occurring to a patient after the patient's participation in the trial has ended, and the investigator believes that the SAE is related to a protocol

procedure or study drug, the investigator should report the SAEs to the sponsor, and the SAEs will be entered in the LSS.

Information on SAEs expected in the study population independent of drug exposure and that will be assessed by the sponsor in aggregate periodically during the course of the trial may be found in the IB.

#### ***10.1.2.1.1. Adverse Event and Serious Adverse Event Reporting***

Data on SAEs that occur before the end of trial will be stored in the collection database and the LSS.

#### ***10.1.2.1.2. Prior to Administration of Study Drug(s)***

During screening, all AEs and SAEs (regardless of relatedness to protocol procedures) are collected after the patient has signed the informed consent form. For patients who do not enroll in the trial (ie, have not received at least 1 dose of ramucirumab and/or LY2875358), only AEs and SAEs related to protocol procedures are required to be collected.

#### ***10.1.2.1.3. On Therapy***

All AEs and SAEs, regardless of relatedness to study drug(s) or protocol procedures, occurring while the patient is receiving study drug must be reported to Lilly or its designee. A patient is considered to be receiving study drug from the time he/she receives the first dose of study drug to when he/she receives the last dose of study drug.

#### ***10.1.2.1.4. Follow-Up Visit***

All AEs and SAEs, regardless of relatedness to study drug(s) or protocol procedures, occurring during the follow-up visit (Visit 801) must be reported to Lilly or its designee. The initial follow-up period (V801) starts following the last dose of LY2875358. At the follow-up visit (V801) ( $30 \pm 3$  days after last dose of LY2875358) the patient will be required to have specific safety assessments ([Attachment 1](#)).

Following the safety assessments, which mark the end of the follow-up visit (Visit 801), the patient will be discontinued from the study, unless there is an ongoing AE or SAE that is possibly related to study drug(s). In this instance, the patient should be followed until the event is resolved, the event is no longer considered to be drug-related, the event becomes stable or returns to baseline, a new treatment is initiated for the patient, or the patient dies or is lost to follow-up.

If it is deemed to be in the best interest of the patient to start a new anticancer treatment prior to the scheduled end of the follow-up visit, the follow-up visit duration may be shortened. In this case, the follow-up assessments should be completed prior to the initiation of the new therapy.

After the follow-up visit (Visit 801), AEs are not required to be reported unless the investigator feels the AEs were related to either study drug(s) or a protocol procedure. If an investigator becomes aware of an SAE believed to be related to protocol procedures or study drug(s), the investigator should report the SAE to the sponsor, and the SAE will be entered in the LSS.

#### **10.1.2.1.5. Suspected Unexpected Serious Adverse Reactions**

Suspected unexpected serious adverse reactions (SUSARs) are SAEs that are not listed in the DCSI of the IB and that the investigator identifies as related to study drug or procedure. The US 21 CFR 312.32, the EU Clinical Trial Directive 2001/20/EC, and the associated detailed guidances or national regulatory requirements in participating countries require the reporting of SUSARs. Lilly has procedures that will be followed for the recording and expedited reporting of SUSARs that are consistent with global regulatory regulations and the associated detailed guidances.

#### **10.1.2.2. Summary of Adverse Event/Serious Adverse Event Reporting Guidelines**

The AE and SAE reporting guidelines are summarized in [Table JTBF.4](#).

**Table JTBF.4. Adverse Event and Serious Adverse Reporting Guidelines for Study JTBF**

Timing	Types of AEs/SAEs Reported	Collection Database	Lilly Safety System
Prestudy (baseline assessments) (Starts at the signing of informed consent and ends just before the first dose of study drug)	Pre-existing conditions All AEs All SAEs regardless of relatedness	x x x	x
On therapy (Starts at first dose of study drug[s] and ends at last dose of study drug[s])	All AEs All SAEs regardless of relatedness	x x	x
Follow-up Visit (Visit 801) (Starts just after the last dose of study drug[s] and ends when end of study safety assessments are completed $30 \pm 3$ days after last dose of study drug[s])	All AEs All SAEs regardless of relatedness	x x	x
Subsequent follow-up visits, if necessary for patient monitoring	Ongoing AEs possibly related to study drug(s), or protocol procedures All SAEs related to protocol procedures or study drug(s)	x x	x
Patient no longer on study	All SAEs related to protocol procedures or study drug of which the investigator becomes aware		x

Abbreviations: AE = adverse event; SAE = serious adverse event.

#### **10.1.3. Other Safety Measures**

##### **10.1.3.1. Electrocardiograms**

For each patient, single 12-lead ECGs will be obtained according to the Study Schedule ([Attachment 1](#)). The patient must be supine for approximately 5 to 10 minutes before ECG

collection and remain supine during ECG collection. Electrocardiograms must be recorded before collecting any blood for safety or PK tests. Electrocardiograms may be obtained at additional times, when deemed necessary (eg, for safety reasons). All recorded ECGs should be stored at the investigational site.

Electrocardiograms will be interpreted by a qualified physician (the investigator or qualified designee) at the site as soon after the time of ECG collection as possible, and ideally while the patient is still present, to determine whether the patient meets entry criteria and for immediate patient management, should any clinically relevant findings be identified.

After enrollment, if a clinically significant finding is identified (including but not limited to changes in QT/QTc interval from baseline), the investigator will determine if the patient can continue in the study. The investigator or qualified designee is responsible for determining if any change in patient management is needed and must document his/her review of the ECG printed at the time of collection. Any new clinically relevant finding should be reported as an AE.

#### **10.1.4. Safety Monitoring**

The Lilly CRP or CRS will monitor safety data throughout the course of the study.

Representatives from Lilly Global Patient Safety will specifically monitor SAEs. Lilly will review SAEs within time frames mandated by company standard operating procedures. The Lilly CRP/CRS will, as is appropriate, consult with the functionally independent Global Patient Safety therapeutic area physician or CRS, and periodically review:

- trends in safety data
- laboratory analytes
- AEs
- If a study patient experiences elevated ALT  $\geq 5$  X ULN and elevated total bilirubin  $\geq 2$  X ULN, clinical and laboratory monitoring should be initiated by the investigator. For patients entering the study with ALT  $\geq 3$  X ULN, monitoring should be triggered at ALT  $\geq 2$  X baseline.

Details for hepatic monitoring depend upon the severity and persistence of observed laboratory test abnormalities. To ensure patient safety and comply with regulatory guidance, the investigator is to consult with the Lilly CRP/CRS regarding collection of specific recommended clinical information and follow-up laboratory tests (see Attachment 3).

#### **10.1.5. Complaint Handling**

Lilly collects complaints on study drugs used in clinical studies in order to ensure the safety of study participants, monitor quality, and facilitate process and product improvements.

Complaints related to concomitant drugs are reported directly to the manufacturers of those drugs in accordance with the package insert.

The investigator or his/her designee is responsible for handling the following aspects of the complaint process in accordance with the instructions provided for this study:

- recording a complete description of the complaint reported and any associated adverse events using the study-specific complaint forms provided for this purpose
- faxing the completed complaint form within 24 hours to Lilly or its designee

If the investigator is asked to return the product for investigation, he/she will return a copy of the product complaint form with the product.

## 10.2. Sample Collection and Testing

[Attachment 1](#) lists the schedule of study evaluations in this study.

[Attachment 2](#) lists the specific laboratory tests that will be performed for this study.

[Attachment 4](#) lists the schedule for PK and PD sample collections in this study.

[Attachment 7](#) provides a summary of the estimated maximum number and volume of invasive samples, for all sampling, during the study.

### 10.2.1. Samples for Study Qualification and Health Monitoring

Tumor tissue, blood, and urine samples will be collected at the times specified in the Study Schedule ([Attachment 1](#)). [Attachment 7](#) summarizes volumes for all invasive sampling (screening, safety evaluations, and bioanalytical markers).

Investigators must document their review of each laboratory safety report.

To meet study eligibility criteria, patients must have available a FFPE tumor specimen taken by core needle biopsy or surgical biopsy prior to study treatment but after progression (or discontinuation) to the most recent line of systemic tumor therapy (“post-progression tumor sample”) or be willing to undergo a tumor biopsy of a pre-study treatment by core needle biopsy or surgical biopsy. Tumor specimen samples may be of any type of tissue, with the exception of bone or CNS metastases. Cytological samples and fine-needle aspiration specimens are not acceptable. Tumor tissue specimens must have adequate evaluable tumor cells. Due diligence should be used to make sure that tumor specimens (not a normal adjacent or a tumor margin sample) are provided. An associated pathology report may also be requested to be sent with the samples. Tumor samples will be labeled with patient number and tissue of origin.

For the “post-progression tumor sample”, submission of a tissue block is preferred.

Alternatively, approximately 15 serially cut unstained sections from the FFPE block can be submitted. If the requested amount of tumor samples from the “post-progression tumor sample” are not available, the patient may still be eligible, upon discussion with the Lilly study team, with the assumption that the patient can provide sufficient tumor tissue specimen for assessment of at least MET expression and VEGFR-2 status.

Blood and urine samples collected for specified laboratory tests will be destroyed within 60 days of receipt of confirmed test results. Tests are run and confirmed promptly whenever scientifically appropriate. When scientific circumstances warrant, however, it is acceptable to retain samples to batch the tests run, or to retain the samples until the end of the study to confirm

that the results are valid. Certain samples may be retained for a longer period, if necessary, to comply with applicable laws, regulations, or laboratory certification standards.

The tumor tissue samples will be coded with the patient number and stored for up to a maximum 15 years after the last patient visit for the study at a facility selected by the sponsor. The samples and any data generated from them can only be linked back to the patient by investigator site personnel. The duration allows the sponsor to respond to regulatory requests related to the study drugs. Tumor specimens submitted as a FFPE tissue block will be returned to the sites by end of study or upon request.

### **10.2.2. Samples for Biomarker Research**

There is growing evidence that genetic variation may impact a patient's response to therapy. Variable response to therapy may be due to genetic determinants that impact drug absorption, distribution, metabolism, and excretion, the mechanism of action of the drug, the disease etiology and/or the molecular subtype of the disease being treated. Therefore, where local regulations and ERBs allow, a blood sample will be collected for pharmacogenetic analysis.

In the event of an unexpected AE or the observation of unusual response, the pharmacogenetic biomarker samples may be genotyped and analysis may be performed to evaluate a genetic association with response to ramucirumab and LY2875358. These investigations may be limited to a focused candidate gene study or, if appropriate, genome-wide analysis may be performed to identify regions of the genome associated with the variability observed in drug response. The pharmacogenetic biomarker samples will only be used for investigations related to disease and drug or class of drugs under study in the context of this clinical program. They will not be used for broad exploratory unspecified disease or population genetic analysis.

Collection of samples for biomarker research and PK/PD analyses is an integral part of this study. Assessments may include analysis of tumor tissue and blood for exploratory biomarkers related to the VEGFR-2 and HGF/MET signaling pathways as well as to biology of the respective tumor types in this study and potential resistance mechanisms. The association of biomarkers with the objectives of the study (including PK/PD biomarker relationship) may be assessed. The exploratory biomarker sampling times are listed in [Attachment 1](#). The exploratory biomarker analysis may be performed by the sponsor or at a laboratory selected by the sponsor.

Samples for exploratory biomarker research to be collected from patients in this study are the following:

- Tumor tissue samples: Mandatory "post-progression tumor samples" and optional tumor samples from any time since diagnosis of the tumor disease (ie, archival tumor samples) may be analyzed for, including but not necessarily limited to, VEGFR-2, MET expression, MET and EGFR amplification, and HGF expression. Optional tissue samples for biomarker research from patients willing to consent to additional on study biopsies should be collected at any time during the study if safe and feasible and upon notification of the sponsor (preferably core tumor biopsies; alternatively, cytology or fine-needle aspiration). In particular, biopsies from patients

progressing on study therapy are encouraged to be performed, provided no other cancer treatment has been started and the procedure does not impede or delay planned cancer treatment.

- Blood samples: Blood samples may be analyzed for, including but not necessarily limited to, circulating levels of VEGF-A, soluble VEGFR-2, PIGF, HGF, and MET-ECD. Blood biomarker levels from the study treatment period may be compared with baseline (screening). In addition, the time course of blood biomarker levels during the study and PK/PD biomarker relationship may be evaluated.

Details for the handling and shipping of tumor biopsy samples will be provided in a separate document. Instructions and supplies required for the collection, processing, and shipment of the patients' tissue and blood samples will be provided by the sponsor.

The samples will be coded with the patient number and stored for up to a maximum 15 years after the last patient visit for the study at a facility selected by the sponsor. The samples and any data generated from them can only be linked back to the patient by investigator site personnel. The duration allows the sponsor to respond to regulatory requests related to the study drug.

Samples will be destroyed according to a process consistent with local regulation.

### **10.2.3. Samples for Drug Concentration Measurements Pharmacokinetics**

Pharmacokinetic samples will be collected as specified in the Pharmacokinetic and Pharmacodynamic Sampling Schedule ([Attachment 4](#)).

#### **10.2.3.1. Pharmacokinetic Samples**

Blood samples will be collected for the analysis of ramucirumab and LY2875358 levels to estimate the PK parameters of both compounds when administered in combination. Furthermore, PK parameters will be assessed for evaluation of PK/PD relationship, and to inform dose escalation.

The PK sampling times are listed in [Attachment 4](#). Up to 5 additional PK samples may be drawn during the study if warranted and agreed upon by both the investigator and sponsor.

Instructions for the collection and handling of blood samples will be provided by the sponsor or central lab. The actual date and time (24-hour clock time) of each sampling will be recorded.

These samples will be analyzed at a laboratory designated by the sponsor. Serum concentrations of LY2875358 and ramucirumab will be assayed using validated enzyme-linked immunosorbent assay methods.

The PK samples will be stored at a facility designated by the sponsor.

The remaining serum from the samples collected for PK may be pooled and used for exploratory biomarker work as deemed appropriate.

Bioanalytical samples collected to measure investigational product concentration will be retained for a maximum of 1 year following last patient visit for the study.

#### **10.2.4. Samples for Immunogenicity Research**

Blood samples for immunogenicity testing will be collected to determine antibody production against study drugs (ramucirumab and LY2875358). Immunogenicity will be assessed by a validated assay designed to detect anti-drug antibodies in the presence of study drugs. Antibodies may be further characterized and/or evaluated for their ability to neutralize the activity of study drugs.

Samples may be stored for a maximum of 15 years following last patient visit for the trial at a facility selected by the sponsor to enable further analysis of immune responses to study drugs. The duration allows the sponsor to respond to regulatory requests related to study drugs.

### **10.3. Efficacy Evaluations**

A secondary objective of the study is to document any antitumor activity. Refer to [Attachment 1](#) for details regarding the timing of specific efficacy measures. Efficacy measures include:

- ORR: The proportion of patients who exhibit a confirmed complete response (CR) or PR relative to baseline as defined by RECIST 1.1 (Eisenhauer et al. 2009)
- DCR: The proportion of patients in the analysis population who exhibit a SD or confirmed CR or PR relative to baseline during the study
- PFS: The time from the date of study enrollment to the date of first observation of objective progression or death from any cause
- Change in tumor size: The change in tumor size from baseline measurement to the measurement with the smallest tumor size during the study.

Each patient will be assessed by one or more of the following radiologic tests for tumor measurement:

- CT scan
- MRI
- Chest x-ray.

Each patient's full extent of disease will also be assessed with:

- Tumor measurement by RECIST 1.1 (Eisenhauer et al. 2009)
- Evaluation of tumor markers, if indicated
- Evaluation of ECOG performance status (refer to [Attachment 6](#)).

Consistent with RECIST, all patients may undergo alternative imaging studies consistent with institutional guidelines to assess tumor response. This may include, but is not limited to, FDG-PET, dynamic contrasted-enhanced MRI, or other modalities.

To confirm objective responses, all lesions should be radiologically assessed, and the same radiologic method used for the initial response determination should be repeated at least 4 weeks following the initial observation of an objective response, using the sample method that was used at baseline. If a patient is discontinued from the study, repeat radiology assessments may be omitted if clear clinical signs of progressive disease are present.

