- f If a patient experiences an infusion-related reaction (see Section 9.2.3.1), immunogenicity samples for anti-ramucirumab and anti-LY2875358 antibodies and PK samples will be taken as close to the onset of the event as possible, at the resolution of the event, and approximately 30 days following the event.
- g The method of assessment used at baseline must be used consistently for tumor assessment and will be repeated approximately every 6 weeks ( $\pm 7$  days) during the study treatment period for lesions outside the CNS. For those patients with known CNS metastases, ongoing CNS surveillance using the same modality is required approximately every 12 weeks ( $\pm 7$  days). Positron emission tomography /CT is allowed if CT portion is of diagnostic quality.
- h For patients in Part B1 (gastric), the mandatory FDG-PET approximately 6 weeks ( $\pm 7$  days) after initiation of study treatment should be performed only if the baseline FDG-PET demonstrated PET avid lesion(s). Further functional tumor imaging (including but not limited to DCE-MRI, FLT-PET) is permitted throughout the study in all patients if appropriate for the respective tumor type at the discretion of the investigator and considered as institutional standard of care or is part of an appropriate imaging study open at the site.

---

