6.3. Handling of Dropouts or Missing Data

Missing data will not be imputed.

In Part B, patients with response that is deemed non-evaluable will be included in the denominator for the purpose of calculating ORR. Non-evaluable patients are patients who do not have a measurable disease at baseline or patients who do not have any post-baseline assessment performed.

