6.12. Efficacy Analyses

As a coprimary objective for Part B, this study will evaluate preliminary antitumor activity observed with ramucirumab in combination with LY2875358 in the tumor-specific expansion cohorts.

Overall Response Rate (ORR): ORR is defined as the proportion of patients who exhibit a confirmed CR or PR relative to baseline as defined by RECIST 1.1 (Eisenhauer et al. 2009).

ORR is computed as the number of responders divided by the total number of treated patients. A responder is defined as any patient who exhibits a confirmed CR or PR relative to baseline

assessment, done on or up to 7 days prior to Cycle 1 Day 1. Patients with response that is deemed not evaluable will be considered non-responders and will be included in the denominator for the purpose of calculating ORR. ORR will be assessed within each cohort, ORR with 95% CIs will be estimated using the Clopper-Pearson method.

Progression-Free Survival (PFS): The PFS time is measured from the date of receiving the first dose of study drug to the date of first objective progression as assessed by the investigator or the date of death due to any cause, whichever is earlier. Table 6.2 provides additional details. The censoring is taken in the following order:

- If a patient does not have a complete baseline disease assessment, then the PFS time will be censored at the enrollment date, regardless of whether or not objectively determined disease progression or death has been observed for the patient; otherwise,
- If a patient is not known to have died or have objective progression as of the data inclusion cutoff date for the analysis, the PFS time will be censored at the last evaluable objective progression-free disease assessment date.

If a patient has a missed visit prior to an event (progression or death), then the PFS time will be censored at the last evaluable assessment prior to the event.

Table 6.2. Definition of PFS

Situation	Outcome	Date of Progression or Censoring
Death before first objective PD assessment	Progressed	Date of death
Objective PD	Progressed	Date of first radiologic assessment showing progressive disease
No evaluable baseline tumor assessments	Censored	Enrollment date
No progression	Censored	Date of last radiologic assessment of measured lesions showing no progression
New systemic anticancer treatment started	Censored	Date of last radiologic assessment of measured lesions showing no progression prior to the commencement of new systemic anticancer treatment

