6.19. Clinical Trial Registry Analyses

Additional analyses will be performed for the purpose of fulfilling the Clinical Trial Registry (CTR) requirements.

Analyses provided for the CTR requirements include the following:

Summary of adverse events, provided as a dataset which will be converted to an XML file. Both Serious Adverse Events and 'Other' Adverse Events are summarized: by treatment group, by MedDRA preferred term.

- An adverse event is considered 'Serious' whether or not it is a treatment emergent adverse event (TEAE).
- An adverse event is considered in the 'Other' category if it is both a TEAE and is not serious. For each Serious AE and 'Other' AE, for each term and treatment group, the following are provided:
 - the number of participants at risk of an event
 - the number of participants who experienced each event term
 - the number of events experienced.
- Consistent with www.ClinicalTrials.gov requirements, 'Other' AEs that occur in fewer than 5% of patients/subjects in every treatment group may not be included if a 5% threshold is chosen (5% is the minimum threshold).
- AE reporting is consistent with other document disclosures for example, the CSR, manuscripts, and so forth.

A participant flow summary will also be produced. This participant flow will describe how many patients in each study part completed the study, and for those who did not, the frequency of each reason for not completing.

- At the time of database lock, the following patients will be considered to have completed the study:
 - any patient enrolled in Part A who completed one cycle of treatment or discontinued due to an adverse event and completed the required safety and full set of PK assessments during cycle 1.
 - any patient enrolled in Parts B1, B2, B3 and B4 who was treated until disease progression (objective or symptomatic) or death, or discontinued due to an

adverse event and completed the required safety assessments during follow up; patient must have measurable disease at baseline and at least one post treatment radiographic assessment per RECIST.

7. References

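### PFS has no rule for symptomatic progression, so unscanned clinical failures are censored; if the expansion landmark is a Kaplan-Meier estimate, it is biased upward

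*Protocol*

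**What the plan says.** **Event and censoring.** Protocol 10.3 ends PFS at "the date of first observation of objective progression or death from any cause". SAP 6.12 agrees. For a patient with neither event known by the data cutoff, it says "the PFS time will be censored at the last evaluable objective progression-free disease assessment date". SAP Table 6.2 has rows for objective progression, death, no progression, new systemic therapy and missed visits, but none for clinical or symptomatic progression.

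**Imaging and follow-up.** Footnote g of Protocol Attachment 1 schedules scans about every 6 weeks "during the study treatment period for lesions outside the CNS". In its paragraph on confirming responses, Protocol 10.3 adds that for a patient discontinued from the study "repeat radiology assessments may be omitted if clear clinical signs of progressive disease are present". Protocol 10.1.2.1.4 places one follow-up visit about 30 days after the last dose, after which "the patient will be discontinued from the study, unless there is an ongoing AE or SAE" possibly related to study drug. Overall survival is not among the efficacy measures in Protocol 10.3.

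**Symptomatic progression is expected.** SAP 6.19 counts as a Part B completer a patient "treated until disease progression (objective or symptomatic) or death", subject to its other conditions.

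**Use of the landmark.** Protocol 8.1.1 allows disease control, as an alternative to response, to support enlarging a cohort from about 15 to about 45 patients. Table JTBF.2 gives the figures: gastric 40% observed and 60% of interest at 12 weeks; the other three cohorts 50% and 75%.

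**The concern.** A patient who stops treatment because the disease is clinically worse is a known failure. Under the PFS rules, unless a scan or a recorded death intervenes, that patient is classed with those who had not progressed and is censored at the last clean scan, or effectively at enrollment if there was no post-baseline scan. Kaplan-Meier then assumes that the patient would have done as well as those still followed. The reason for leaving is the disease itself, so the assumption fails in a known direction.

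What is at stake is the landmark comparison that may help open a cohort to about 30 more patients. The gastric cohort is the most exposed: only two scheduled scans fall by week 12, and a patient who fails clinically before week 6 contributes no follow-up at all. ORR does not share the problem, because under SAP 6.3 "patients with response that is deemed non-evaluable will be included in the denominator".

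**Working it through.** **The plan's own false-go figure.** Protocol 8.1.1 gives one only for the response rule with 15 patients: 1 − 0.97^15 = 36.7% at a true response rate of 3%, and 1 − 0.90^15 = 79.4% at 10%. Both reproduce (stated as 36.7% and 79%). No such figure is given for the landmark route, so it has to be derived.

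**Inputs from the documents.** Historical and target landmarks (Table JTBF.2), 6-weekly scans (Attachment 1), about 15 patients per cohort (8.1.1). An exponential curve with the gastric median PFS of 2.1 months (5.2.1.1) gives 12-week PFS of 0.5^(2.76/2.1) = 40.2%, against 40% in the table, so an exponential model is reasonable there.

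**Assumptions.** A share f of failures is clinical only, unscanned, and censored at the previous scan. The documents give no value for f. The landmark is read from a Kaplan-Meier curve.

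**Formula.** Let S be the true landmark PFS, k the number of scan intervals to the landmark, and q = 1 − S^(1/k) the chance of failing in one interval. Clinical-only failures leave the risk set at the start of their interval, so the apparent survival per interval is (1 − q)/(1 − qf). The expected landmark estimate is S/(1 − qf)^k.

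**Gastric.** S = 0.40 and k = 2, so q = 1 − √0.40 = 0.3675.
- f = 0.1: 0.40/(1 − 0.03675)² = 0.40/0.928 = 43%
- f = 0.2: 0.40/(1 − 0.0735)² = 0.40/0.858 = 47%
- f = 0.3: 0.40/(1 − 0.1103)² = 0.40/0.792 = 51%

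Simulation (40,000 trials of 15 patients per setting) agrees with these means and gives the chance of reaching 60%. The last two columns assume that 30% of the clinical-only patients die within 30 days and that those deaths count as events.

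| f | Estimate | Chance of 60% or more | Estimate, deaths counted | Chance, deaths counted |
|---|---|---|---|---|
| 0 | 40% | 10% | 40% | 10% |
| 0.1 | 43% | 12% | 42% | 11% |
| 0.2 | 47% | 17% | 45% | 15% |
| 0.3 | 51% | 26% | 48% | 20% |

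At f = 0 the exact binomial check, at least 9 of 15 at 40%, is 9.5%.

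**HCC, RCC and NSCLC** (true 50%, target 75%). Without clinical-only failures the chance of reaching the target is 1.8% (at least 12 of 15). At f = 0.1, 0.2 and 0.3 the expected estimate is about 53%, 57% and 60 to 61%, and the chance about 4%, 9% and 15%.

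**Other estimators.** If the gastric landmark is instead a proportion of all treated patients, with those censored early counted as failures, it stays at 40% for every f. If clinical progression is counted as an event, it also returns to 40%, with the 9.5% chance above.

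**The case against.** **The scan waiver is narrow.** A reader might infer that Protocol 10.3 excuses the scan for any patient with clinical progression. The sentence closes a paragraph on confirming responses and most naturally covers confirmatory scans. This stands. The point does not need the sentence, because no scan is scheduled at or after discontinuation in any case.

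**No estimator is specified.** Kaplan-Meier appears only in the SAP reference list, efficacy analyses include everyone dosed, and Protocol 8.1.1 calls the trigger disease control. This stands in part. The table entries are labelled PFS and the SAP writes censoring rules for PFS, so Kaplan-Meier is the natural reading, but the upward bias is conditional on it.

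**Follow-up is not absent.** A reader might infer that these patients are never followed for death. Deaths up to about day 30 are captured and can be events, and SAP 6.12 also requires a later documented progression date to be recorded. This stands and reduces the size, as the table shows. The protection is uncertain, however. The SAP text says that after a missed visit before an event "then the PFS time will be censored at the last evaluable assessment prior to the event", while Table 6.2 requires more than one missed visit; the text version could remove some of those deaths.

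**Nothing is triggered mechanically.** Expansion is a matter of judgement and agreement, and discontinuation reasons are listed (SAP 6.7). This stands: the probabilities describe a fixed threshold, which the plan does not impose.

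**The benchmarks may share the convention.** The documents do not say how the historical trials handled clinical progression. If they censored it too, part of the bias cancels. This can be neither assumed nor excluded. For NSCLC the benchmark is a docetaxel arm, so a comparison with ramucirumab alone does not apply there.

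**Conclusion.** The gap is real and the direction is clear under Kaplan-Meier: known clinical failures can be censored in the PFS estimate that may support expansion. For gastric, assumed clinical-only shares of 10% to 30% move a true 40% to about 43% to 51%, and less if early deaths are counted. These figures rest on an exponential model, an unspecified estimator, an assumed share and a discretionary trigger.

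A reader might go further and infer that an inactive combination would routinely appear to meet the gastric target, since five clinical-only failures before the first scan among 15 patients give 6/(15 − 5) = 60%. The documents do not support that. About 15 × 0.3675 = 5.5 failures are expected before week 6, so the example needs roughly 91% of them to be unscanned with no recorded death, in a population selected for ECOG 0 to 1 and a life expectancy allowing 8 weeks of treatment. Nor is the different handling of ORR a contradiction: a proportion and a time-to-event measure may treat missing data differently. This is a worthwhile, cheap improvement, not an invalidating flaw.

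**What to change.** In SAP 6.12:
- Name the estimator for the Table JTBF.2 landmark.
- For the expansion review, report beside the objective-only PFS landmark a second estimate that counts discontinuation for symptomatic progression as an event at its recorded date. Give the number of patients affected, and require both estimates to be considered before a cohort is enlarged.
- Keep patients who stop for toxicity or other reasons without progression censored. Requiring a progression-free scan at the landmark from every treated patient would wrongly fail these patients, and the 4-month and 7.1-month landmarks do not fall on the 6-weekly scans.
- Reconcile the missed-visit rule in the text with Table 6.2.

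The cost is SAP wording and one tabulation, since the reason for and date of discontinuation are already collected (Protocol 8.2.1). No treatment rule changes. The downside is that the second estimate will be no higher than the first, lower whenever it reclassifies a patient before the landmark, and may not be like-for-like with the historical PFS figures. That is why it accompanies the objective-only estimate and does not replace it.
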